### 7.3.3. Subgroup Analyses for the Coprimary Endpoints

Subgroup analysis will be performed for the coprimary endpoints based on the following participant demographics and baseline disease characteristics variables for those participants whose data are available:

- Baseline EASI score ( $\geq 16$ ,  $< 16$ )
- Age (18 to  $< 65$  years,  $\geq 65$  years)
- Sex (male, female)
- Race
- Geographic region (Europe vs ROW)
- Prior systemic or phototherapy (yes or no)
- Season the participant was enrolled

Season the participant was enrolled will be defined as below:

- Spring: March to May (Northern Hemisphere) and September to November (Southern Hemisphere).
- Summer: June to August (Northern Hemisphere) and December to February (Southern Hemisphere).
- Fall: September to November (Northern Hemisphere) and March to May (Southern Hemisphere).
- Winter: December to February (Northern Hemisphere) and June to August (Southern Hemisphere).

### **7.3.4. Sensitivity and Supportive Analyses for the Coprimary Endpoints**

#### **7.3.4.1. Longitudinal Logistic Regression With Repeated Measures**

To adjust for the dependence underlying the hierarchical multilevel data structure (visit, participant, and site), a longitudinal logistic regression with repeated measures will be applied in both of the coprimary endpoints. The 3 level structures in the model are as follows:

- Level 1: visit
- Level 2: participant
- Level 3: site

where visits are nested within participants, which are further nested within sites.

The binary response (IGA-TS or EASI75) of each participant at Week 2, Week 4, and Week 8 will be included as the dependent variable. Treatment (1.5% BID and vehicle BID), the randomization stratification factors (baseline EASI and geographic region), visit, and treatment-by-visit interaction will be included as fixed effects. Site level intercept and participant nested in site level intercept will be included as random effects. The within-participant and within-site errors will be modeled by an unstructured variance-covariance matrix. The Kenward-Roger approximation will be used to estimate denominator degrees of freedom for this model.

#### **7.3.4.2. Multiple Imputation**

Multiple imputation will be used as an alternative method to handle missing data. A full conditional specification method ([van Buuren 2007](#)) that assumes the existence of a joint distribution for all variables will be used to impute the IGA or EASI score. A regression model including treatment group, stratification factors and baseline and scheduled postbaseline scores up to Week 8 will be specified for the fully conditional specification method. The imputation will be repeated a number of times to generate corresponding complete datasets in order to reflect the uncertainty around the true values. An example of the multiple imputation SAS code is provided in [Appendix B](#). The coprimary endpoints binary response will be derived for each of the imputed datasets per the definition in Sections 7.3.1.1 and 7.3.1.2. Regardless of MI imputed values, subjects with a missing Week 8 IGA and EASI assessments after discontinuation from treatment due to lack of efficacy or adverse event will be counted as nonresponders. The CMH test in Section 7.3.2 will be applied to each of the imputed datasets. The results will then be combined for the inference using Rubin's rule for each of the coprimary endpoints.

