6.5.2. Criteria for Permanent Discontinuation of Study Cream

Participants must permanently discontinue study cream if they meet any of the following criteria:

- Occurrence of an AE that is related to treatment with the study cream that, in the judgment of the investigator or the medical monitor, compromises the participant's ability to continue study-specific procedures or is considered to not be in the participant's best interest
- Worsening of AD that requires treatment with a prohibited concomitant medication
- Any Grade 4 laboratory abnormality (see [Table 7](#)) considered related to the study cream
- Persistent AE requiring an interruption of study cream for more than 2 weeks without resolution of the AE

See Section [7](#) for discontinuation procedures.

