7. DISCONTINUATION OF STUDY TREATMENT AND PARTICIPANT WITHDRAWAL

7.1. Discontinuation of Study Treatment

7.1.1. Reasons for Discontinuation

Participants **must** be discontinued from study treatment for the following reasons:

- Lack of efficacy response during the VCE period (defined as no change/improvement in %BSA, IGA score, or EASI score when treated with ruxolitinib cream in the escape arm continuously for 8 weeks).
- AD worsens during either the VC period or the VCE period (including the escape arm), to the point where the extent of AD to be treated (ie, all areas excluding the scalp) exceeds 20% BSA.
- The participant becomes pregnant.
- Consent is withdrawn.

Note: Consent withdrawn means that the participant has explicitly indicated that they do not want to be followed any longer; in this case, no further data, except data in the public domain, may be solicited from or collected on the participant. Participants may choose to discontinue study treatment and remain in the study to be followed for safety monitoring.

- Further participation would be injurious to the participant's health or well-being, in the investigator's medical judgment.
- Any AE of unacceptable severity as noted in Section 6.5.2.
- The study is terminated by the sponsor.
- The study is terminated by the local health authority, IRB, or IEC.

A participant **may** be discontinued from study treatment as follows:

- Participants who are noncompliant with study cream (see Section 6.4) or who use more than one 60-g tube per 4 days will have the application instructions reinforced by the investigator or a qualified designee. Participants who after 2 consecutive study visits and reinforcement of study cream application instructions by site staff again fail to meet compliance benchmarks or again use more than one 60-g tube per 4 days may be considered for withdrawal from the study. The medical monitor should be consulted for instruction on handling the participant.
- If, during the course of the study, a participant is found not to have met eligibility criteria, the sponsor's medical monitor or delegate, in collaboration with the investigator, will determine whether the participant should be withdrawn from study treatment.
- If a participant is noncompliant with study procedures (eg, completion of eDiary), the sponsor's medical monitor (or designee) should be consulted for instruction on handling the participant.

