
• Any safety assessments (eg, electrocardiogram, vital signs measurements), including those that worsen from baseline, considered clinically significant in the medical and scientific judgment of the investigator (ie, not related to disease progression) are to be reported as an AE.• Abnormal laboratory test results are to be reported as an AE if they are considered clinically meaningful, induce clinical signs or symptoms, require concomitant therapy, or require changes in study cream. Whenever possible, a diagnosis (eg, anemia, thrombocytopenia) should be recorded in the eCRF rather than the abnormal laboratory test result (eg, low hemoglobin, platelet count decreased).• Exacerbation of a chronic or intermittent pre-existing condition/disease, including either an increase in the frequency and/or intensity of the condition, is to be reported as an AE.• New conditions detected or diagnosed after the start of study cream administration are to be reported as an AE.• New signs and/or symptoms due to the study disease that develop after the first dose of study cream are to be captured on the appropriate efficacy CRF. Any worsening of the underlying disease that is more severe than expected for the participant's condition is to be reported as an AE.• Signs, symptoms, or the clinical sequelae of a suspected drug-drug interaction are to be reported as an AE.• Signs and/or symptoms from dose administration errors of a study cream (eg, overdose) or a concomitant medication are to be reported as an AE.• "Lack of efficacy," "disease progression," or "failure of expected pharmacological action" will not be reported as an AE or SAE. Such instances will be captured in the efficacy assessments.• A condition that leads to a medical or surgical procedure (eg, endoscopy, appendectomy) will be reported as an AE if it occurs after obtaining informed consent. If the condition is present before entering the study, then it should be captured as medical history.• Pre-existing diseases, pre-existing conditions, or new conditions with expected fluctuations in signs or symptoms should be reported as an AE only if the investigator judges the fluctuation to have worsened more than expected during study participation.

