## APPENDIX B. SAS CODE FOR MULTIPLE IMPUTATION

The following sample SAS code will be used for the MI of IGA:

```
proc mi data=mi_wide seed=184243261 nimpute=40 out=impute_IGA;  
  class trt01p strat1 strat2;  
  var trt01p strat1 Strat2 avalBASELINE avalWEEK2 avalWEEK4 avalWEEK8;  
  fcs REGPMM;  
  
run;
```

The following sample SAS code will be used for the MI of EASI:

```
proc mi data=mi_wide seed=184243262 nimpute=40 out=impute_EASI;  
  class trt01p strat1 strat2;  
  var trt01p strat1 Strat2 avalBASELINE avalWEEK2 avalWEEK4 avalWEEK8;  
  fcs;  
  
run;
```

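### The multiple-imputation sensitivity analysis does not secure nonresponder status for participants taken off cream for worsening AD before Week 8

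*SAP*

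**What the plan says.** **The MI rule.** SAP 7.3.4.2 imputes missing IGA and EASI scores by fully conditional specification: "A regression model including treatment group, stratification factors and baseline and scheduled postbaseline scores up to Week 8 will be specified". The sample code in SAP Appendix B uses treatment, the two strata and "avalBASELINE avalWEEK2 avalWEEK4 avalWEEK8", with 40 imputations. Neither place has a term for discontinuation or its reason. After imputation, one exception applies: participants missing Week 8 "after discontinuation from treatment due to lack of efficacy or adverse event will be counted as nonresponders".

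**The protocol's stops.**
- Section 7.1.1 lists one stop under that name: "Lack of efficacy response during the VCE period (defined as no change/improvement in %BSA, IGA score, or EASI score when treated with ruxolitinib cream" continuously for 8 weeks in the escape arm. It cannot arise before Week 8.
- A separate entry in the same list, also set out in Section 6.1, requires stopping in the vehicle-controlled (VC) period once the area to be treated exceeds 20% BSA.
- Section 6.5.2 adds "Worsening of AD that requires treatment with a prohibited concomitant medication", listed apart from its adverse event criteria.

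**The adverse event route.** Section 9.1 says that lack of efficacy and disease progression "will not be reported as an AE or SAE. Such instances will be captured in the efficacy assessments". The same section makes worsening of the disease beyond what was expected for that participant a reportable AE.

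**The primary analysis.** SAP 7.3.2 and the estimand in SAP Table 4 count discontinuation before Week 8 for any reason as nonresponse.

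**The concern.** The override shows that the sponsor does not want outcome-related stops imputed as if treatment had continued. The reasons it names do not match the headings under which the protocol stops a participant whose AD worsens in the VC period. If such a stop is recorded under another reason, the missing Week 8 score is drawn from a model that includes treatment and knows nothing about why the participant left. A ruxolitinib participant with no postbaseline score would then get roughly the ruxolitinib arm's response chance.

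The imputation may also miss the worsening itself. Protocol 8.8 says that early-termination evaluations replace those of a coinciding scheduled visit and go on the ET pages. The SAP gives no rule for placing an ET1 score at Week 2, 4 or 8. This is an open point rather than a demonstrated loss, since protocol Table 3 puts ET1 in the Week 8 column.

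What is at stake is the value of the robustness check. Protocol 10.4.1 mentions a tipping point analysis as optional, and SAP 7.3.4 does not take it up. The per-protocol analysis drops participants with missing coprimary data. The only missing-data sensitivity tables in SAP Appendix A are the two MI tables (2.1.2 and 2.2.2).

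**Working it through.** **Inputs.** From protocol 10.1 and Table 9: 225 participants randomized 2:1, so 150 and 75; EASI75 70% vs 15%; IGA-TS 60% vs 10%; 2-sided alpha 0.05; Fisher exact test. The documents give no rate of stopping for worsening, so the shares below are assumptions.

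**1. The plan's own figure.** Exact Fisher power at 150 vs 75 is above 99.9% for EASI75 and IGA-TS, and 99.98%, 99.6%, 99.1% and 97.8% for ITCH4 at Week 8, Day 7, Day 3 and Day 2. The stated power above 95% reproduces throughout.

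**2. Does a VC-period worsening stop reach the override?**

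| Stop | Through lack of efficacy | Through adverse event |
|---|---|---|
| Treated area above 20% BSA | Only if the site codes it so | Only if worse than expected |
| Worsening needing a prohibited medication | Only if the site codes it so | Only if worse than expected |

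Protocol 7.1.2 requires the primary reason in the eCRF, but the list of reasons is not in the documents. Neither route is secured by the SAP text.

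**3. Size with equal stopping.** Let p be the response rate among participants who do not stop, d the share stopping for worsening, and q their chance of being imputed a responder. The arm's rate is p(1 − d) + dq. Counting them as nonresponders sets q = 0. With no postbaseline score in the model, q is about p. The difference is then overstated by d(p_rux − p_veh), when shares and timing are the same in both arms.

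At d = 5%, EASI75 under nonresponse is 70 × 0.95 = 66.5% vs 15 × 0.95 = 14.25%, a difference of 52.25 points. Imputed at the arm rate it stays at 55.0.

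| d, each arm | EASI75 difference: imputed / nonresponse | Overstated by | IGA-TS difference: imputed / nonresponse | Overstated by |
|---|---|---|---|---|
| 2% | 55.0 / 53.9 | 1.1 | 50.0 / 49.0 | 1.0 |
| 5% | 55.0 / 52.25 | 2.75 | 50.0 / 47.5 | 2.5 |
| 10% | 55.0 / 49.5 | 5.5 | 50.0 / 45.0 | 5.0 |

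**4. Unequal stopping.** The overstatement becomes d_rux × p_rux − d_veh × p_veh.
- 2% on ruxolitinib and 5% on vehicle, EASI75: 1.40 − 0.75 = 0.65 points.
- 5% and 10%, EASI75: 3.5 − 1.5 = 2.0 points.
- It is zero when vehicle participants stop 70/15 = 4.7 times as often (EASI75) or 60/10 = 6 times as often (IGA-TS), and reverses beyond that.
- Stopping on ruxolitinib alone at 5% would give 0.05 × 70 = 3.5 points, so the table is a ceiling only for equal shares and timing.

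**5. How q depends on the scores available.** An illustrative simulation of EASI used normal-regression imputation on treatment, baseline and available visits, with 40 imputations and 200 trials. Assumptions were baseline EASI of about 14 (SD 4), percent improvement with SD 30 set to give 70% and 15% EASI75, and stoppers last seen with EASI 30% above baseline. Strata were left out, and IGA was not simulated.

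| Postbaseline scores in the model | Imputed EASI75, ruxolitinib | Imputed EASI75, vehicle |
|---|---|---|
| None | 62% | 11% |
| Worsened Week 2 | 5% | 0.3% |
| Worsened Weeks 2 and 4 | about 0% | about 0% |

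Five ruxolitinib stops would add 5 × 0.62 / 150 = 2.1 points to that arm's rate with no postbaseline score, but only 5 × 0.05 / 150 = 0.2 points with a worsened Week 2 score.

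**The case against.** The strongest reply is that lack of efficacy in SAP 7.3.4.2 is an ordinary disposition category and does not refer to the escape-arm rule in protocol 7.1.1. Read narrowly, that half of the override would be empty before Week 8, so the broad reading is the more natural one, and sites may well code worsening stops that way. This stands as a possibility. It is not secured, because the SAP does not define the term and the reason list is not available.

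Three stronger readings are tempting, and the documents do not support them.
- *No worsening stop can enter as an adverse event.* Protocol 9.1 excludes disease progression but makes worsening more severe than expected an AE. Some of these stops would be overridden.
- *Every 20% BSA stop is a documented treatment failure.* Under protocol 6.1, baseline areas stay under treatment even after they resolve, and new areas are added to them. For example, a participant with 18% at baseline, largely cleared, and 3% of new area reaches 21% and must stop without necessarily failing on EASI or IGA.
- *The analysis is shown to favor ruxolitinib.* With equal stopping it does, because treatment is in the imputation model. The net direction depends on stopping rates that the documents do not give.

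It is also fair to say that MI is a sensitivity analysis which protocol 10.4.1 describes as optional.

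**Conclusion.** The gap is real and limited. SAP 7.3.4.2 does not map the protocol's two VC-period worsening stops to its nonresponder override, so whether these participants are imputed or counted as failures depends on site coding. The effect is confined to the MI sensitivity analysis and is material mainly for stops with no postbaseline score in the model.

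If 5% of each arm stopped this way at similar times, the overstatement is at most 2.75 points for EASI75 and 2.5 points for IGA-TS. It is 1.1 and 1.0 points at 2%, and 5.5 and 5.0 points at 10%. These shares are assumptions, and unequal stopping could shrink or reverse the effect.

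A reader might infer that the coprimary result is at risk. It is not: the primary analysis counts any discontinuation as nonresponse, and against planned differences of 55 and 50 points no reversal of the conclusion is plausible. The change is still worth making, because a robustness check should not leave the handling of worsening to how a reason happens to be coded.

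**What to change.** In SAP 7.3.4.2, extend the override so that, in every imputed dataset, missing Week 8 scores count as nonresponse after any discontinuation for AD worsening (treated area above 20% BSA, or need for a prohibited AD medication), as well as for lack of efficacy or an adverse event. Add a table mapping each eCRF discontinuation reason to this rule, and fix it before unblinding at the primary database lock. For these participants it then no longer matters whether an ET1 score reaches the imputation model.

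The cost is one sentence and a short mapping table. The primary reason for stopping is already collected, although whether the eCRF list separates these reasons cannot be checked from the documents. MI response rates become slightly lower. A few participants stopped on cumulative treated area despite improvement would be counted conservatively as nonresponders, which is consistent with the primary estimand. No clinical rule changes.

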### **7.4. Analysis of the Key Secondary Efficacy Parameters**

#### **7.4.1. Key Secondary Efficacy Measures**

##### **7.4.1.1. Itch Numerical Rating Scale Score**

The Itch NRS is a once-daily patient-reported measure of itch intensity assessed using an 11-point scale (0 = no itch to 10 = worst imaginable itch) that best describes their worst level of itching in the past 24 hours.

The Itch NRS score for baseline will be determined by averaging the 7 daily NRS scores directly before Day 1 (Day -7 to Day -1). The by-visit Itch NRS score for postbaseline visits will be determined by averaging the 7 daily NRS scores directly before the visit day. If 4 or more daily scores are missing (out of the 7), the Itch NRS score at the visit will be set to missing. For all daily itch related analyses, including time to achieve Itch NRS score improvement of at least 2 or 4 points analyses, baseline will be defined as the last available Itch NRS score during the week prior to Day 1 (Day -7 to Day -1).

The proportion of participants with a clinically relevant change in itch, defined as a  $\geq 4$ -point improvement in Itch NRS score from baseline to Week 8, will be summarized by treatment group for participants with baseline Itch NRS score  $\geq 4$ .

#### **7.4.2. Key Secondary Efficacy Analysis**

Key secondary efficacy analyses will be conducted in the ITT population in the VC period. If the coprimary endpoints are both achieved, the statistical comparisons for key secondary endpoints will be tested with the procedures specified in Section 3.2. The same nonresponder imputation method as specified in the primary analysis will be used to handle missing Week 8 itch data, and the CMH test described in Section 7.3.2 will be applied to compare 1.5% BID arm and the vehicle cream group for the key secondary endpoint of  $\geq 4$ -point improvement in Itch NRS score response at Week 8. For the key secondary endpoints of Itch NRS score responses on Day 7, Day 3 and Day 2, all participants who are missing Day 7, Day 3, and/or Day 2 daily Itch NRS scores will be imputed using multiple imputation by fully conditional specification method. The variables to be included in the imputation regression model are treatment group, stratification factors, baseline itch score, and postbaseline daily itch score on Day 1 to Day 7. The corresponding binary response on Day 7, Day 3, and Day 2 will be derived for each of the imputed datasets per the definition in Section 7.4.1.1. The CMH test specified in Section 7.3.2 will be applied to each imputed dataset and then the results will be combined for the inference using Rubin's rule.

### **7.5. Analysis of Secondary Efficacy Parameters**

#### **7.5.1. Secondary Efficacy Measures**

##### **7.5.1.1. Body Surface Area**

Total %BSA affected by AD will be estimated at each visit in the VC and VCE period. Body surface area assessment will be approximated to the nearest 0.1% using the handprint (Palmar) method as a guide. The approximate size of the participant's entire palmar surface (ie, the palm plus 5 digits, with fingers tucked together and thumb tucked to the side) should be considered as 1% BSA, and the approximate size of the participant's thumb should be considered as 0.1% BSA.

#### **7.5.1.2. SCORing Atopic Dermatitis**

The SCORAD is a tool to assess the extent and severity (ie, intensity) of eczema and will be completed before, during, and after treatment has begun to determine whether the treatment has been effective. This will be performed during all VC and VCE period study visits, starting at baseline.

- To determine extent, the rule of 9 or handprint method is used to calculate the eczema affected area (A) as a percentage of the whole body. Scores are added up to give a possible maximum of 100%.
- To determine intensity, a representative area of eczema is selected. The intensity of redness, swelling, oozing/crusting, scratch marks, skin thickening (lichenification), dryness (this is assessed in an area where there is no inflammation) is assessed individually as follows:
  - None (0)
  - Mild (1)
  - Moderate (2)
  - Severe (3)

Intensity scores are added together to give "B" (maximum score of 18).

- Subjective symptoms, that is, itch and sleeplessness, are scored by the participant using a visual analog scale where "0" is no itch (or no sleeplessness) and "10" is the worst imaginable itch (or sleeplessness).

These scores are added to give "C" (maximum score of 20).

Total score gives approximate weights of 60% to intensity and 20% each to extent and subjective signs (ie, insomnia) for the participant and will be calculated as follows:  $A/5 + 7B/2 + C$ .

#### **7.5.1.3. Current Itch Numeric Rating Scale**

On the morning of Day 1 (if the participant qualifies for randomization into the study) visit only, participants will be asked to evaluate the current intensity of their itch at the following assessment times: directly before initial study cream application and 5, 15, 30, 45, and 60 minutes as well as 2, 4, and 6 hours post-study cream application. The 6-hour assessment should be performed prior to the evening study cream application. Participants will be asked to rate the current itch severity of their AD by selecting a number from on a scale from 0 to 10, with 0 indicating no itch and 10 indicating the worst itch imaginable. Baseline of the current Itch NRS will be defined as the current itch score right before the initial study cream application.

